17.7. Registration of Study and Disclosure of Study Results

Bioverativ will register the study and post study results regardless of outcome on a publicly accessible website in accordance with the applicable laws and regulations.

CONFIDENTIAL

The information contained herein may not be used, disclosed, or published without the written consent of Bioverativ Therapeutics Inc

18. ADMINISTRATIVE PROCEDURES

18.1. Study Site Initiation

The Investigator must not screen any subjects prior to completion of a study initiation visit, conducted by Bioverativ or designee. This initiation visit will include a detailed review of the protocol and study procedures.

18.2. Quality Assurance

During and/or after completion of the study, quality assurance officers named by Bioverativ or the regulatory authorities may wish to perform on-site audits or inspections. The Investigator will be expected to cooperate with any audit or inspection and to provide assistance and documentation (including source data) as requested.

18.3. Monitoring of the Study

The Investigator must permit study-related monitoring by providing direct access to source data and to the subjects' medical histories.

The Clinical Monitor(s) will visit the Investigator(s) at regular intervals during the study and after the study has completed, as appropriate.

During these visits, eCRFs and supporting documentation related to the study will be reviewed and any discrepancies or omissions will be resolved.

The monitoring visits must be conducted according to the applicable ICH and GCP guidelines to ensure protocol adherence, quality of data, study treatment accountability, compliance with regulatory requirements, and continued adequacy of the investigational site and its facilities.

18.4. Study Funding

Bioverativ is the Sponsor of the study and is funding the study. All financial details are provided in the separate contract(s) between the institution, Investigator, and Bioverativ.

18.5. Publications

Details are included in the clinical trial agreement for this study.

CONFIDENTIAL

The information contained herein may not be used, disclosed, or published without the written consent of Bioverativ Therapeutics Inc

19. FURTHER REQUIREMENTS AND GENERAL INFORMATION

19.1. External Contract Organizations

19.1.1. Contract Research Organization

A contract research organization (CRO) will be responsible for administrative aspects of the study including, but not limited to, study initiation, monitoring, management of SAE reports, data management, and the coordination of an independent external DSMC. Before subjects are screened at each study site, the CRO will review study responsibilities with the Investigators and other study site staff, as appropriate.

19.1.2. Interactive Voice and Web Response System

An IXRS will be used in this study. Before subjects are screened or enrolled, the appropriate training will be provided to the study staff by the Sponsor and the IXRS vendor. A user manual will also be provided. Specific details regarding IXRS are provided in the Study Reference Manual.

19.1.3. Electronic Data Capture

Subject information will be captured and managed by study sites on eCRFs by a web-based electronic data capture tool developed and supported by the CRO assisting with the conduct of the study and configured by Bioverativ. Data should be entered into the electronic data capture tool within 5 business days.

In addition, subjects/parents/caregivers in the study will have EPDs to record information regarding each dose of rFIXFc administered to the subject for any reason at their home or locations other than the study site. The subject or the subject's parent/caregiver must enter dosing information into the EPD *as soon as possible after an injection and within a maximum of 7 days following the injection*, to ensure data integrity, and to facilitate appropriate medical review and dosing guidance. It is recommended that subjects or parents/caregivers enter dosing information immediately after an injection (Section 10.1.2).

19.1.4. Central Laboratories for Laboratory Assessments

Central laboratories have been selected by the Sponsor to analyze all the laboratory samples being collected in the study. Specifics regarding the requirements for laboratory specimen collection, handling, and analysis are provided in the Laboratory Manuals.

19.2. Study Committees

19.2.1. Independent Data Safety Monitoring Committee

An independent external DSMC is responsible for evaluating and monitoring the safety and tolerability of the study drug on an ongoing basis during the study. The specifics regarding the DSMC organization and procedures will be outlined in the DSMC Charter.

CONFIDENTIAL

The information contained herein may not be used, disclosed, or published without the written consent of Bioverativ
Therapeutics Inc

19.3. Changes to Final Study Protocol

All protocol amendments must be submitted to the ethics committee and Regulatory Authorities if required by local law. Protocol modifications that affect subject safety, the scope of the investigation, or the scientific quality of the study must be approved by the ethics committee before implementation of such modifications to the conduct of the study. If required by local law, such modifications must also be approved by the appropriate regulatory agency prior to implementation.

However, Bioverativ may, at any time, amend this protocol to eliminate an apparent immediate hazard to a subject. In this case, the appropriate regulatory authorities will be notified subsequent to the modification.

In the event of a protocol modification, the subject consent form may require similar modifications (see Sections [17.2](#) and [17.3](#)).

19.4. Ethics Committee Notification of Study Completion or Termination

Where required, the Health Authorities and ethics committees must be notified of completion or termination of this study, and sent a copy of the study synopsis in accordance with necessary timelines.

19.5. Retention of Study Data

The minimum retention time for study records will meet the strictest standard applicable to that site, as dictated by any institutional requirements or local laws or regulations. Prior to proceeding with destruction of records, the Investigator must notify Bioverativ in writing and receive written authorization from Bioverativ to destroy study records. In addition, the Investigator must notify Bioverativ of any changes in the archival arrangements including, but not limited to, archival at an off-site facility or transfer of ownership if the Investigator leaves the site.

19.6. Study Report Signatory

Bioverativ will designate one of the participating Study Investigators as a signatory for the study report. This determination will be made by several factors, including, but not limited to, the Investigator's experience and reputation in the studied indication, the Investigator's contribution to the study in terms of design, management, and/or subject enrollment, or by other factors determined to be relevant by Bioverativ.

Bioverativ will follow all applicable local regulations pertaining to study report signatories.

CONFIDENTIAL

The information contained herein may not be used, disclosed, or published without the written consent of Bioverativ
Therapeutics Inc

APPENDIX A. rFIXFc DOSING GUIDELINES FOR BLEEDING EPISODES

The Sponsor will review, analyze, and interpret FIX activity results from the central laboratory. Based on this review, the Sponsor will make a recommendation to the Investigator for the appropriate dose selection for the corresponding individual and treatment situation. The following table describes dosing guidance with rFIXFc for bleeding episodes.

DOSING GUIDELINES FOR rFIXFc THERAPY IN HEMOPHILIA B

Type of Hemorrhage	Factor IX Level Required (%)
Minor	
Epistaxis	25-30
Hemarthroses, uncomplicated	25-30
Superficial muscular	25-30
Superficial soft tissue	25-30
Moderate	
Epistaxis	35-50
Intramuscular with dissection	35-50
Soft tissue with dissection	35-50
Mucous membranes	35-50
Dental extractions	35-50
Hematuria	35-50
Hemarthroses, with limited motion	35-50
Major	
Epistaxis	60-100
Pharynx	60-100
Retropharynx	60-100
Retroperitoneum	60-100
Surgery	60-100
Central nervous system	60-100

CONFIDENTIAL

The information contained herein may not be used, disclosed, or published without the written consent of Bioverativ Therapeutics Inc

APPENDIX B. ASSESSMENT OF RESPONSE TO BLEEDING

[REDACTED]

■ [REDACTED]

■ [REDACTED]

■ [REDACTED]

■ [REDACTED]

[REDACTED]

CONFIDENTIAL

The information contained herein may not be used, disclosed, or published without the written consent of Bioverativ
Therapeutics Inc

APPENDIX C. PHYSICIAN'S GLOBAL ASSESSMENT

[REDACTED]

■ [REDACTED]

■ [REDACTED]

■ [REDACTED]

■ [REDACTED]

[REDACTED]

■ [REDACTED]

■ [REDACTED]

■ [REDACTED]

CONFIDENTIAL

The information contained herein may not be used, disclosed, or published without the written consent of Bioverativ Therapeutics Inc

**APPENDIX D. PHYSICIAN ASSESSMENT OF RESPONSE TO
TREATMENT DURING SURGERY**

[REDACTED]

[REDACTED]

| [REDACTED]

| [REDACTED]

| [REDACTED]

[REDACTED]

| [REDACTED]

| [REDACTED]

[REDACTED]

| [REDACTED]

| [REDACTED]

| [REDACTED]

[REDACTED]

| [REDACTED]

| [REDACTED]

| [REDACTED]

[REDACTED]

| [REDACTED]

CONFIDENTIAL

The information contained herein may not be used, disclosed, or published without the written consent of Bioverativ
Therapeutics Inc

█ [REDACTED]

█ [REDACTED]

CONFIDENTIAL

The information contained herein may not be used, disclosed, or published without the written consent of Bioverativ
Therapeutics Inc

## LIST OF ABBREVIATIONS

ABR	Annualized Bleeding Rate
AE	Adverse Event
ALT/SGPT	Alanine Aminotransferase
AST/SGOT	Aspartate Aminotransferase
BU	Bethesda Units
BUN	Blood Urea Nitrogen
CHMP	Committee for Medicinal Products for Human Use
CI	Confidence Interval
C max	Maximum Plasma Activity/Concentration
CRO	Contract Research Organization
CS	Clinically Significant
CSR	Clinical Study Report
CTCAE	Common Toxicity Criteria for Adverse Events
dL	Deciliter
DSMC	Data Safety Monitoring Committee
eCRF	Electronic Case Report Form
ED	Exposure Day
EMA	European Medicines Agency
EOS	End of Study
EOT	End of Treatment
EPD	Electronic Patient Diary
ET	Early Termination
FAS	Full Analysis Set
FIX	Coagulation Factor IX
FU	Follow-up
GGT	Gamma Glutamyl Transferase
IR	Incremental Recovery
ITI	Immune Tolerance Induction
IU	International Unit

IXRS	Interactive Voice/Web Response System
L	Litre
LLN	Lower Limit of Normal
LLOQ	Lower Limit of Quantification
MedDRA	Medical Dictionary for Regulatory Activities
MHRA	Medicines and Healthcare products Regulatory Agency
mL	Millilitre
mmol	Millimole
NCS	Not Clinically Significant
PD	Plasma Derived
PK	Pharmacokinetic
PRO	Patient Reported Outcome
PT	Preferred Term
PTP	Previously Treated Patient
PUP	Previously Untreated Patient
RBC	Red Blood Cell Count
rFIXFc	Recombinant Coagulation Factor IX Fc Fusion Protein
SAE	Serious Adverse Event
SAP	Statistical Analysis Plan
SB	Spontaneous Bleed
SD	Standard Deviation
SOC	System Organ Class
SVC	Single Vial Consolidation
TEAE	Treatment Emergent Adverse Event
TB	Traumatic Bleed
ULN	Upper Limit of Normal
ULOQ	Upper Limit of Quantification
WBC	White Blood Cell Count
WHO	World Health Organization

	Statistical Analysis Plan	Final v1.0
---	----------------------------------	-------------------

## **1. INTRODUCTION**

Study 998HB303 is a Phase 3, open label, single arm, multicenter study designed to evaluate the safety and efficacy of recombinant coagulation factor IX Fc fusion protein (rFIXFc; BIIB029) in the prevention and treatment of bleeding in previously untreated male patients < 18 years of age with severe hemophilia B, in accordance with the EMA CHMP guideline on clinical investigation of recombinant and human plasma-derived factor IX products.

This statistical analysis plan (SAP) will describe the final analysis of 998HB303 study data when at least 20 patients have reached at least 50 EDs with rFIXFc.

This SAP is based on Version 3 of the approved study protocol dated 06 August 2018 and more complete details of the study can be found therein.

## **2. STUDY OBJECTIVES AND ENDPOINTS**

### **2.1. Study Objectives**

#### **2.1.1. Primary Objective**

The primary objective of the study is to evaluate the safety of rFIXFc in previously untreated patients (PUPs) with severe hemophilia B.

#### **2.1.2. Secondary Objectives**

The secondary objectives of this study are:

- To evaluate the efficacy of rFIXFc in the prevention and treatment of bleeding episodes in PUPs.
- To evaluate rFIXFc consumption for the prevention and treatment of bleeding episodes in PUPs.

#### **2.1.3. Exploratory Objectives**

The exploratory objective of this study is to evaluate the effect of rFIXFc based on patient-reported outcomes (PROs) and health resource utilization.

### **2.2. Study Endpoints**

#### **2.2.1. Primary Endpoint**

The primary endpoint of this study is the occurrence of inhibitor development.

#### **2.2.2. Secondary Endpoints**

The secondary endpoints of the study are as follows:

- The annualized number of bleeding episodes per patient (annualized bleeding rate [ABR]).
- The annualized number of spontaneous joint bleeding episodes per patient.
- Assessments of response to treatment with rFIXFc for bleeding episodes, using the 4-point bleeding response scale (Investigator assessment for bleeding episodes treated in the clinic; parent or caregiver assessment for all other bleeding episodes).
- Total number of EDs per patient per year.
- Total annualized rFIXFc consumption per patient for the prevention and treatment of bleeding episodes.
- The number of injections and dose per injection of rFIXFc required to resolve a bleeding episode.
- rFIXFc incremental recovery (IR).

### **2.2.3. Exploratory Endpoints**

The exploratory endpoints include, but are not limited to:

- Health outcomes.

### **2.2.4. Pharmacokinetic Endpoints**

The only pharmacokinetic (PK) endpoint in this study is rFIXFc IR, as specified in Section [2.2.2](#).

### **2.2.5. Pharmacodynamic Endpoints**

There is no pharmacodynamic endpoint in this study.

	Statistical Analysis Plan	Final v1.0
---	----------------------------------	-------------------

### **3. STUDY DESIGN**

#### **3.1. Overall Study Design and Plan**

This study is open label, single arm, and multicenter, designed to evaluate the safety and efficacy of rFIXFc in PUPs with severe hemophilia B when used according to local standard of care for implementation of a prophylactic regimen, including an optional preceding episodic (on-demand) treatment regimen.

The study period consists of screening, treatment, and follow-up. Individual patient study participation is expected to be approximately 6 months to 3 years including screening and follow-up. The treatment period comprises 3 possible regimens: An optional episodic regimen; a prophylactic regimen required for all patients; and an immune tolerance induction (ITI) regimen only for patients who develop inhibitors.

Approximately 30 patients will be enrolled to achieve at least 20 patients with no less than 50 EDs by the end of the study. One ED is defined as a 24-hour period in which a patient receives one or more doses of rFIXFc, with the time of the first injection of rFIXFc defined as the start of the ED.

##### **3.1.1. Study Sample**

Patient inclusion and exclusion criteria can be found in [Sections 8.1](#) and [8.2](#) of the protocol.

##### **3.1.2. Treatment Arms**

This is a single-arm study. All patients will be treated with study drug rFIXFc.

Within this single arm, there are 3 possible treatment regimens: An optional episodic (on-demand) regimen; a required prophylactic regimen for all patients; and an ITI regimen available only for patients who develop an inhibitor as defined in [Section 3.1.2.3](#).

###### **3.1.2.1. Episodic Treatment Regimen**

Once eligibility has been confirmed and the subject has been enrolled, the Investigator has the option to treat the subject episodically, until a prophylactic regimen is initiated. Dosing will be determined by the Investigator using the guidelines in [Appendix A](#) of the approved protocol. The duration of episodic treatment is at the Investigator's discretion. Date of transition from episodic treatment to prophylactic treatment is captured on the study electronic case report form (eCRF).

###### **3.1.2.2. Prophylactic Treatment Regimen**

The use of a prophylactic treatment regimen in young children is currently the recommended standard of care in hemophilia due to the demonstrated benefit on long-term outcomes. It is anticipated that patients will begin a prophylactic treatment regimen prior to or immediately following the occurrence of a third hemarthrosis (joint bleed). The recommended initial prophylactic regimen is 50 IU/kg weekly. Adjustments to the dose and dosing interval can be made based upon available incremental recovery data, subsequent FIX activity levels, level of

	Statistical Analysis Plan	Final v1.0
---	----------------------------------	-------------------

physical activity, and bleeding pattern, in accordance with local standards of care for a prophylactic regimen.

Prophylactic treatment will continue until the patient reaches at least 50 EDs to study drug, discontinues, begins an ITI regimen, or the end of study is declared by Bioverativ.

### **3.1.2.3. Immune Tolerance Induction (ITI) Treatment Regimen**

Immune tolerance induction (ITI) with rFIXFc is allowed during the study for those subjects developing a positive high-titer inhibitor or a positive low-titer inhibitor (both defined in Section 5.2.4) with poorly controlled bleeding. The Medical Monitor will work with the Investigator to ascertain an established ITI regimen of the Investigator's choice. The ITI regimen plan must be approved for each subject by Bioverativ's Study Medical Director. A separate consent is required before starting the ITI regimen.

Duration of ITI treatment is up to 24 months, or until the criteria for successful immune tolerance are met. The criteria for successful immune tolerance are described in Section 10.2.6.5 of the protocol. Patients who choose to discontinue ITI prior to meeting the criteria for success will be withdrawn from the study.

### **3.1.3. End of Study**

End of the study (EOS) will occur when at least 20 patients have reached at least 50 EDs with rFIXFc and had at least one inhibitor test performed at or beyond 50 EDs.

### **3.1.4. Independent Data Monitoring Committee**

An independent, external Data Safety Monitoring Committee (DSMC) is responsible for evaluating and monitoring the safety and tolerability of the study drug on an ongoing basis during the study. The specifics regarding the DSMC organization and procedures are outlined in the DSMC Charter.

## **3.2. Statistical Hypothesis**

There is no statistical hypothesis for this study as all but the primary endpoint will be analyzed descriptively only. The methodology for analysis of the primary endpoint is described in Section 9.4.3.

## **3.3. Sample Size Justification**

The planned total sample size for this study is approximately 30 patients.

Because the size of the hemophilia population is limited, the sample size is based on clinical rather than statistical considerations. Taking into account the CHMP Guideline and in an effort to enroll a sufficient number of patients to assess the efficacy and safety of rFIXFc in this population of primarily very young children, approximately 30 patients will be enrolled to achieve at least 20 patients with no less than 50 EDs by the completion of the study.

	Statistical Analysis Plan	Final v1.0
---	----------------------------------	-------------------

### **3.4. Randomization and Blinding**

This is an open-label single arm study so there is no blinding or randomization.

### **3.5. Interim Analysis**

No interim analysis is planned for this study.

	Statistical Analysis Plan	Final v1.0
---	----------------------------------	-------------------

## **4. ANALYSIS POPULATIONS**

### **4.1. All-Enrolled Analysis Set**

The All-Enrolled Analysis Set is defined as all patients who were enrolled in the study, whether dosed with rFIXFc or not. Patients will be considered enrolled when the Investigator has verified that they are eligible according to the criteria in [Sections 8.1, 8.2 and 8.3](#) of the protocol.

Patient disposition summaries, enrollment summaries and all patient data listings will be based on the All-Enrolled Analysis Set, unless otherwise stated in this SAP.

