The Baseline IR Visit assessments should be performed as soon as practicable once all eligibility criteria have been met and the subject has been enrolled. The Baseline IR Visit activities (Section 4.2.1) may be completed on the same day as Screening, or they may be completed as part of a separate visit or at an unscheduled visit. Baseline IR assessments must be performed when the subject is in a non-bleeding state, after at least a 72 hour washout. Eligible subjects will report to the study site for administration in the clinic of the Baseline IR Visit dose of 50 IU/kg by actual potency (see the Directions for Handling and Administration [DHA] and Section 10.1.1 of this protocol for further information on actual potency dosing). The dose will be delivered via a slow push IV injection over several minutes, at a rate of administration determined by the subject's comfort level. Subjects will be required to complete the assessments according to Section 4.2.1, including collection of FIX activity samples for the calculation of incremental recovery.

Bleeding episodes that occur prior to meeting all eligibility criteria should be treated with commercially available rFIXFc. If a subject requires more than 3 injections of commercially available rFIXFc prior to confirmation of eligibility, the subject will be considered a screen failure. In countries where rFIXFc is not yet commercially available, any bleeding episode that occurs prior to meeting eligibility criteria should be treated with another FIX concentrate and the subject will be considered a screen failure. After meeting eligibility criteria, all bleeding episodes should be treated with rFIXFc study drug. The Baseline IR Visit may be delayed until the subject is in a non-bleeding state and a 72-hour washout period may be safely performed.

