15.1.2.1. Serious Pretreatment Event

A serious pretreatment event is any event that meets the criteria for SAE reporting (as defined in Section 15.1.2) and occurs after signing of the ICF, but before administration of rFIXFc (commercially available rFIXFc or study drug). A serious pretreatment event is to be reported on the SAE Form and faxed to Quintiles Pharmacovigilance within 24 hours of the study site staff becoming aware of the event (see Section 15.3.3); such an event will be recorded in the eCRF.

Any serious adverse event that occurs after the first dose of commercially available rFIXFc but prior to signing of the ICF should be reported as a post-marketing event; such an event will not be considered a serious pretreatment event and will not be recorded in the eCRF.

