16.5.2.2. Adverse Events

AEs will be coded using the Medical Dictionary for Regulatory Activities. The incidence of AEs will be summarized by system organ class and preferred term. Summaries will be for all AEs as well as by severity and relationship to treatment. Subject listings will be provided for all AEs, SAEs, AEs resulting in discontinuation of study treatment and/or from the study, and deaths.

Unless otherwise specified in the study SAP, AEs and SAEs occurring during treatment with the ITI regimen will be summarized and listed separately. Serious pretreatment events will be included and identified in the SAE listing, but only serious events occurring after the start of treatment will be summarized.

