### **4.2. Safety Analysis Set**

The Safety Analysis Set is defined as all patients who received at least 1 dose of study rFIXFc. All analyses and summaries of safety, demographics, and baseline characteristics will be based on the Safety Analysis Set, unless otherwise specified in this SAP.

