#### **5.4.5. Safety Period**

The overall safety period is defined as beginning at the first dose of study medication rFIXFc. For patients who are subsequently enrolled, the safety period ends on the date of the Final Safety Follow-up Visit (by telephone or in person), 14 (+7) days after the last dose of rFIXFc. For patients who fail screening, this period ends on the date that this is confirmed.

The safety period on a specific treatment regimen is as described in Section 5.3 except that the end of the patient's last treatment regimen is the end of their safety period.

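### By default the SAP's AE, SAE and death listings cover enrolled patients only, so events in consented or commercially dosed children who never enroll would be left out, contrary to protocol 16.5.2.2

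*SAP*

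**What the plan says.** **SAP.** Section 4.1 sets the listing population: "all patient data listings will be based on the All-Enrolled Analysis Set", unless the SAP states otherwise. It also fixes who is in that set: "Patients will be considered enrolled when the Investigator has verified that they are eligible according to the criteria in" protocol Sections 8.1, 8.2 and 8.3. Section 9.3 provides listings of all AEs, all SAEs, AEs leading to discontinuation or withdrawal, and deaths (also 9.3.7 to 9.3.9), without naming a population. Section 4.2 requires study drug for the safety population: "The Safety Analysis Set is defined as all patients who received at least 1 dose of study rFIXFc". Section 5.4.5 nevertheless foresees patients who have a safety period and are not enrolled: "For patients who fail screening, this period ends on the date that this is confirmed". Section 9.4.3.1 lists inhibitor test data for every patient.

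**Protocol.** Section 16.5.2.2 asks for subject listings of all AEs, SAEs and deaths and adds: "Serious pretreatment events will be included and identified in the SAE listing". Section 15.1.2.1 defines the term: "A serious pretreatment event is any event that meets the criteria for SAE reporting", with onset between consent and the first rFIXFc dose of either supply. It requires these events to be recorded in the eCRF. Section 16.5.1 counts a child given only commercial rFIXFc in the Safety Analysis Set.

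**The concern.** Safety recording starts at consent, but the default listing population starts at enrollment. Between the two are children with events in the database and no listing that shows them.

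The gap is foreseeable. Consent may precede birth, and screening may run 8 weeks plus a further 8 (protocol 7.3.1). Where commercial rFIXFc is unavailable, a bleed before eligibility "should be treated with another FIX concentrate and the subject will be considered a screen failure". More than 3 commercial injections before eligibility is confirmed is also a screen failure (7.3.1), and hypersensitivity to any rFIXFc is an exclusion (8.2). A safety-relevant event can therefore be the reason a child never enrolls.

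The study plans about 30 patients and its primary objective is safety. At that size, a single unlisted death, serious bleed or reaction would be a material omission from the report.

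**Working it through.** No calculation decides this point. The check takes each group of children and asks where the documents put their events.

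| Group | In All-Enrolled (SAP 4.1)? | In SAP Safety Analysis Set (4.2)? | What the protocol asks |
|---|---|---|---|
| A. Consented, no rFIXFc, never enrolled | No | No | Serious events recorded in the eCRF (15.1.2.1) and placed in the SAE listing (16.5.2.2) |
| B. Consented, commercial rFIXFc only, never enrolled | No | No, as worded | Member of the protocol Safety Analysis Set (16.5.1); AEs and SAEs after consent recorded (15.3.1, 15.3.2) and listed (16.5.2.2) |
| C. Study drug given, then central-laboratory failure | Yes: enrollment is registered before study drug is dispensed (9.1.3) | Yes | Withdrawn, not un-enrolled (8.3, 11); listed |
| D. Enrolled, event between consent and first dose | Yes | Once given study drug | Listed and flagged (SAP 9.3) |

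**Step 1: which rule governs the AE, SAE and death listings.** The 4.1 default yields only where the SAP states otherwise. Where the SAP wants another listing population it names one: the FAS for study drug (6.6), the Surgery Subgroup for major surgery (5.2.5), the ITI Subgroup for ITI data (5.2.5) and all patients for inhibitor data (9.4.3.1). Section 9.3 says that all AEs and SAEs are listed, which describes the events and names no population. The default therefore applies. If SAP 9.1 were read as moving these listings to the Safety Analysis Set, groups A and B would still be outside, because 4.2 requires study drug.

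**Step 2: whether the protocol's listing is wider.** It carries no enrollment condition. A subject number is assigned whether or not the child proves eligible (9.1), and SAEs are reported whether or not study treatment was received (15.3.3). In the protocol's usage, groups A and B are subjects with reportable events.

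**Step 3: whether the departure is declared.** SAP 10 lists three major differences from the protocol. None concerns the listing population.

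**Step 4: limits.** Events after a commercial dose but before consent are post-marketing reports and are not in the eCRF (15.1.2.1, 15.3.1), so no study listing could show them. Inhibitor data have their own statement in 9.4.3.1, which conflicts with the 4.1 default only if it is not read as an exception.

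**Size.** The documents give no screen-failure count. Purely as an assumption, 0 to 4 such children beside 30 enrolled gives 0/30 = 0%, 2/32 = 6.3% and 4/34 = 11.8% of children outside the listings. These are shares of children, not of children with events.

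**The case against.** **The SAP already lists all AEs and SAEs and flags those before first treatment; enrolled children also have a consent-to-dose interval, so protocol 16.5.2.2 has content without screen failures.** This is the best counter-argument, and it is true that 16.5.2.2 does not mention screen failures. But the protocol sets no enrollment condition. The restriction comes from SAP 4.1, and general wording about all events does not clearly lift it.

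**The SAP's safety tables remain backed by listings.** This stands. With study drug required in 4.2 and enrollment preceding study drug, everyone in those tables is in All-Enrolled. A mismatch between tables and listings would arise only under the protocol's wider Safety Analysis Set.

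**SAP 5.4.5 starts the safety period at the first study-medication dose, so it says little about commercial dosing.** This stands in part. Yet its separate ending for screen failures, and its reference to patients enrolled subsequently, make sense only if dosing can precede enrollment.

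**Deaths and discontinuations are also tabulated (SAP 9.3.2 and 12), and expedited SAE reporting is untouched.** Both are true. The tables rest on the Safety Analysis Set, so they do not reach groups A and B either. A never-enrolled child cannot discontinue study drug, so the discontinuation listing matters little here.

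**Children without rFIXFc exposure say nothing about rFIXFc safety.** This is fair for group A as to attribution. It does not answer the protocol's reporting commitment and does not apply to group B.

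**Conclusion.** The point holds for AEs, SAEs (including serious pretreatment events) and deaths of children in groups A and B. Under the SAP default these events drop out of the listings, against protocol 16.5.2.2, and the departure is undeclared. It is a small gap in completeness of safety reporting. It leaves the primary analysis as the SAP defines it unchanged.

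This assumes that the all-events wording in SAP 9.3 is not itself an exception to 4.1 and that enrollment precedes study drug as protocol 9.1.3 requires. The number of children affected is unknown and may be zero.

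A reader might infer more than the documents support:

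- **That every listing is restricted.** SAP 4.1 is a default that allows exceptions, and the SAP uses them.
- **That inhibitor results are lost.** SAP 9.4.3.1 lists them for every patient; only its precedence over 4.1 needs confirming. Nor does enrollment wait for the central inhibitor result (protocol 8.3), so a child positive on that sample is normally enrolled, withdrawn and listed.
- **That dosed children in general are omitted.** Only those given commercial rFIXFc and never enrolled are.
- **That the most serious events are the ones dropped.** Any bleed treated with another FIX concentrate causes screen failure, serious or not.
- **That 6% to 12% of children are missing.** That range rests entirely on an assumed count.

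**What to change.** Add one sentence to SAP 4.1 (or 9.3): the AE, SAE and death listings, and the inhibitor listing for consistency with 9.4.3.1, cover all consented patients with recorded data. Each patient is flagged as consented only, commercial rFIXFc but not enrolled, or enrolled. All-Enrolled remains the default for other listings.

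The cost is that sentence and one flag variable in listings already planned. The data are already collected in the eCRF, and no table or estimate changes. If the sponsor prefers to keep the restriction, SAP 10 should declare it as a departure from protocol 16.5.2.2.
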